Appendix

- Inclusion/Exclusion Checklist
- Makley Sleep Scale Form
- Berlin Questionnaire
- Del-R-98, Question 1 Form
- Functional Independence Measure (FIM)TM
- PANAS
- Karolinska Sleepiness Scale
- Barrow Neurological Institute Fatigue Scale
- Quarterly Staff Survey (a.k.a. Clinician Feasibility Survey)
- Overview of Study Figure

TWILIGHT Study Inclusion and Exclusion Checklist

Inclusion Criteria

Must meet all of the criteria below

- Have experienced a moderate to severe TBI. Defined by any of the following:
 - 1) Loss of Consciousness greater than 30 minutes.
 - 2) Emergency Room admission with a Glasgow Coma Scale of 12 or below.
 - 3) Intracranial abnormalities on imaging.
 - 4) Post-traumatic amnesia that lasts more than 24 hours.
- Admitted to acute inpatient rehabilitation unit at Harborview Medical Center within 3 months of their Traumatic Brain Injury.
- Able to communicate in English.
- Between the ages of 18 and 70 years old

Exclusion Criteria

Unable to enroll if any of the following are true

- Complete blindness
- Absence of eye opening or disorders of consciousness (Rancho level 1-3)
- Does not have sleep disturbance (rating of "0" on item one of the *DeIRS-R98*. If has a rating of "0", but if taking sleep medication in the last 72 hours, then include)
- Tetraplegia with less than antigravity strength in all myotomes caudal to C6 level given the limitations on measuring movements with actigraphy in this population (i.e. cannot reliably detect upper extremity or lower extremity movement with this level of paralysis).
- Past medical history of retinal pathology
- Past medical history of light sensitivity
- Past medical history of narcolepsy
- Past medical history of bipolar disorder
- Past medical history of obstructive sleep apnea
- Suspected sleep apnea. (Determined by administering the Berlin questionnaire)
- Current medical orders indicated for night time sleep disruption (e.g. chest PT, MIE q2 hours of meds that disrupt sleep)". For these subjects, may re-approached if the medical orders are no longer in place.

TWILIGHT STUDY

Was watch verified as on? Staff Initials _____

Date: _____

Makley Sleep Scale Form Clinician rating

Time	Rounding Initials	Sleep Rating Given Observation in the Last Hour (circle)			
2200		0	1	2	3
2300		0	1	2	3
0000		0	1	2	3
0100		0	1	2	3
0200		0	1	2	3
0300		0	1	2	3
0400		0	1	2	3
0500		0	1	2	3
0600		0	1	2	3
Ratings:		Asleep	Drowsy/falling asleep	Drowsy/waking up	awake

Where there any adverse events or effects?

Yes No

Source: _____

If yes, please explain _____

Makley Sleep Log guidelines and FAQ's

Data collection

1. The sleep log can be collected by nurses or MA staff
2. Clinical staff will do data collection rounding on an hourly basis and rate the patient accordingly with a 0,1,2 or 3
3. The rating for each hour is the clinical staff's best assessment of observed sleep/non-sleep state based on how they were found, not what was being done clinically, if anything
4. Hourly ratings may be collected on paper or electronically
5. Sleep log for the first night, along with any and all information about the participant's sleep over the last 3 nights will be used to randomize. Information about the participant's sleep will be asked of any family or friends' present, clinical staff, medical chart review, and nursing notes. Please look to see if the participant has or is on any sleep medications in the past 72 hours.
6. Once the research staff has all information, they will rate the participant using the DelRS-98 item #1 to score their severity of sleep
7. Data may need to be used to reconcile actigraphy data if there are questions
8. Research staff should collect the sleep logs on a daily basis and place a copy in the participants file (de-identified)

FAQ's

1. Clinically what's the difference between 1 (falling asleep) and 2 (waking up) in the setting of night time rounds? Can we tell? **Answer:** Make your best clinically assessment. If patient is fully asleep then score = 0, if patient is fully awake then score = 3.
2. What do we do with missing hours on a sleep log? **Answer:** note it as missing data; follow-up with staff training/study education.
3. What do we do when a sleep log is entirely missing? **Answer:** keep looking to see if it can be found; include notation in case notes; follow-up with staff training/study education.
4. Staff says a patient slept fine but family notes the patient was restless overnight, what data do we take for rating of sleep disturbance in the study? **Answer:** Clinically we know that patients/subjects will be observed at different time points and that the type and quality of observations will be variable. Research staff should collect all available data and make their best summary of presence/absence of ANY sleep changes and if present the rating of severity (using the Del-RS-R 98 item 1) considering that this type of data is generally additive to describe what's happened overnight and not necessarily either/or. To score a subject as having no sleep disturbance there should be no clinical data that says the patient didn't sleep perfectly well (i.e. patient/caregiver/family report is all that sleep was fine, no medications given).

BERLIN QUESTIONNAIRE

Height (m) _____ Weight (kg) _____ Age _____ Male / Female

Please choose the correct response to each question.

CATEGORY 1

1. Do you snore?

- a. Yes
- b. No
- c. Don't know

If you snore:

2. Your snoring is:

- a. Slightly louder than breathing
- b. As loud as talking
- c. Louder than talking
- d. Very loud – can be heard in adjacent rooms

3. How often do you snore

- a. Nearly every day
- b. 3-4 times a week
- c. 1-2 times a week
- d. 1-2 times a month
- e. Never or nearly never

4. Has your snoring ever bothered other people?

- a. Yes
- b. No
- c. Don't Know

5. Has anyone noticed that you quit breathing during your sleep?

- a. Nearly every day
- b. 3-4 times a week
- c. 1-2 times a week
- d. 1-2 times a month
- e. Never or nearly never

CATEGORY 2

6. How often do you feel tired or fatigued after your sleep?

- a. Nearly every day
- b. 3-4 times a week
- c. 1-2 times a week
- d. 1-2 times a month
- e. Never or nearly never

7. During your waking time, do you feel tired, fatigued or not up to par?

- a. Nearly every day
- b. 3-4 times a week
- c. 1-2 times a week
- d. 1-2 times a month
- e. Never or nearly never

8. Have you ever nodded off or fallen asleep while driving a vehicle?

- a. Yes
- b. No

If yes:

9. How often does this occur?

- a. Nearly every day
- b. 3-4 times a week
- c. 1-2 times a week
- d. 1-2 times a month
- e. Never or nearly never

CATEGORY 3

10. Do you have high blood pressure?

- a. Yes
- b. No
- c. Don't know

Rating Sleep-Wake cycle disturbance:

Question 1 is utilized in this study

DELIRIUM RATING SCALE-R-98 (DRS-R-98)

This is a revision of the Delirium Rating Scale (Trzepacz et al. 1988). It is used for initial assessment and repeated measurements of delirium symptom severity. The sum of the 13 item scores provides a severity score. All available sources of information are used to rate the items (nurses, family, chart) in addition to examination of the patient. For serial repeated ratings of delirium severity, reasonable time frames should be chosen between ratings to document meaningful changes because delirium symptom severity can fluctuate without interventions.

DRS-R-98 SEVERITY SCALE

1. Sleep-wake cycle disturbance

Rate sleep-wake pattern using all sources of information, including from family, caregivers, nurses' reports, and patient. Try to distinguish sleep from resting with eyes closed.

0. Not present
1. Mild sleep continuity disturbance at night or occasional drowsiness during the day
2. Moderate disorganization of sleep-wake cycle (e.g., falling asleep during conversations, napping during the day or several brief awakenings during the night with confusion/behavioral changes or very little nighttime sleep)
3. Severe disruption of sleep-wake cycle (e.g., day-night reversal of sleep-wake cycle or severe circadian fragmentation with multiple periods of sleep and wakefulness or severe sleeplessness.)

2. Perceptual disturbances and hallucinations

Illusions and hallucinations can be of any sensory modality. Misperceptions are "simple" if they are uncomplicated, such as a sound, noise, color, spot, or flashes and "complex" if they are multidimensional, such as voices, music, people, animals, or scenes. Rate if reported by patient or caregiver, or inferred by observation.

0. Not present
1. Mild perceptual disturbances (e.g., feelings of derealization or depersonalization; or patient may not be able to discriminate dreams from reality)
2. Illusions present
3. Hallucinations present

3. Delusions

Delusions can be of any type, but are most often persecutory. Rate if reported by patient, family or caregiver. Rate as delusional if ideas are unlikely to be true yet are believed by the patient who cannot be dissuaded by logic. Delusional ideas cannot be explained otherwise by the patient's usual cultural or religious background.

0. Not present
1. Mildly suspicious, hypervigilant, or preoccupied
2. Unusual or overvalued ideation that does not reach delusional proportions or could be plausible
3. Delusional

4. Lability of affect

Rate the patient's affect as the outward presentation of emotions and not as a description of what the patient feels.

0. Not present
1. Affect somewhat altered or incongruent to situation; changes over the course of hours; emotions are mostly under self-control
2. Affect is often inappropriate to the situation and intermittently changes over the course of minutes; emotions are not consistently under self-control, though they respond to redirection by others
3. Severe and consistent disinhibition of emotions; affect changes rapidly, is inappropriate to context, and does not respond to redirection by others

5. Language

Rate abnormalities of spoken, written or sign language that cannot be otherwise attributed to dialect or stuttering. Assess fluency, grammar, comprehension, semantic content and naming. Test comprehension and naming nonverbally if necessary by having patient follow commands or point.

0. Normal language
1. Mild impairment including word-finding difficulty or problems with naming or fluency
2. Moderate impairment including comprehension difficulties or deficits in meaningful communication (semantic content)
3. Severe impairment including nonsensical semantic content, word salad, muteness, or severely reduced comprehension

SELF CARE ITEMS:

ADMISSION DISCHARGE

1. Feeding		
2. Grooming		
3. Bathing		
4. Dressing Upper Body		
5. Dressing Lower Body		
6. Toileting		

SPHINCTER CONTROL:

8. Bladder Management		
a. Level of assistance.....		
b. Frequency of accidents.....		
9. Bowel Management		
a. Level of assistance.....		
b. Frequency of accidents.....		

MOBILITY ITEMS:

Transfer Technique

10. Bed, Chair, Wheelchair		
11. Toilet		
12. Tub or Shower		

Locomotion

14a. Walking on admission		
14b. Wheelchair on admission		
14. Walking/Wheelchair-discharge (w/c/9)		
15. Stairs		

7=Complete Independence (Timely, safely)
 6=Modified Independence (Extra time, device)
 5=Supervision (pt does 100%)
 4=Minimal Assistance (pt ≥75% of task)
 3=Moderate Assistance (pt 50-74% of task)
 2=Maximum Assistance (pt 25-49% of task)
 1=Total Assistance (pt <25% of task)
 0=Activity does not occur. (Use only at admission and only for #1-6,10-15; else use code "9".)
 8=N/A, pt walking/not using wheelchair. (only for item #14b)
 9=Unknown / assessed at >72 hours / activity does not occur (see instructions in code "0", above).
 66=Data not available with new (1/1/02) scoring. (Use only at admission and only for #1-8a, 9, 9a, 10-15)

Use with 8b and 9b
 7=No accidents
 6=No accidents; uses device (catheter, ostomy)
 5=One accident in the past 7 days
 4=Two accidents in the past 7 days
 3=Three accidents in the past 7 days
 2=Four accidents in the past 7 days
 1=Five or more accidents in the past 7 days
 9= Unknown / assessed at >72 hours
 66=Variable did not exist

COMMUNICATIONS:

17. Comprehension ... (a/v/b/9)				
18. Expression (v/n/b/9)				

PSYCHOSOCIAL ADJUSTMENT ITEMS:

22. Social Interaction		
------------------------------	--------------------------	--------------------------

COGNITIVE FUNCTION:

26. Problem Solving		
27. Memory		

PANAS Questionnaire

This scale consists of a number of words that describe different feelings and emotions. Read each item and then list the number from the scale below next to each word. Indicate to what extent you feel this way right now, that is, at the present moment *OR* indicate the extent you have felt this way over the past week (circle the instructions you followed when taking this measure)

1	2	3	4	5
Very Slightly or Not at All	A Little	Moderately	Quite a Bit	Extremely

- | | |
|-----------------------|----------------------|
| _____ 1. Interested | _____ 11. Irritable |
| _____ 2. Distressed | _____ 12. Alert |
| _____ 3. Excited | _____ 13. Ashamed |
| _____ 4. Upset | _____ 14. Inspired |
| _____ 5. Strong | _____ 15. Nervous |
| _____ 6. Guilty | _____ 16. Determined |
| _____ 7. Scared | _____ 17. Attentive |
| _____ 8. Hostile | _____ 18. Jittery |
| _____ 9. Enthusiastic | _____ 19. Active |
| _____ 10. Proud | _____ 20. Afraid |

Scoring Instructions:

Positive Affect Score: Add the scores on items 1, 3, 5, 9, 10, 12, 14, 16, 17, and 19. Scores can range from 10 – 50, with higher scores representing higher levels of positive affect. Mean Scores: Momentary = 29.7 (*SD* = 7.9); Weekly = 33.3 (*SD* = 7.2)

Negative Affect Score: Add the scores on items 2, 4, 6, 7, 8, 11, 13, 15, 18, and 20. Scores can range from 10 – 50, with lower scores representing lower levels of negative affect. Mean Score: Momentary = 14.8 (*SD* = 5.4); Weekly = 17.4 (*SD* = 6.2)

Copyright © 1988 by the American Psychological Association. Reproduced with permission. The official citation that should be used in referencing this material is Watson, D., Clark, L. A., & Tellegan, A. (1988). Development and validation of brief measures of positive and negative affect: The PANAS scales. Journal of Personality and Social Psychology, 54(6), 1063–1070.

BASELINE

Pt. not able to report

Sleepiness Scale: (Karolinska Sleepiness Scale)

Here are some descriptors about how alert or sleepy you might be feeling right now. Which one corresponds to the statement describing how you feel at this moment?

- i. Extremely alert
- ii. Very alert
- iii. Alert
- iv. Rather Alert
- v. Neither alert nor sleepy
- vi. Some signs of sleepiness
- vii. Sleepy, but no difficulty remaining awake
- viii. Sleepy, some effort to keep alert

Pre Light Treatment

Date: _____

Score: _____

BASELINE

Barrow Neurological Institute Fatigue Scale

Pt. not able to report

[figure not shown]
Please rate the extent to which each of the items below has been a problem for you since your injury. You should choose only ONE number from 0-7 on the scale below when making your response.

0	1	2	3	4	5	6	7
Rarely a problem		Occasional problem but not frequent		A Frequent Problem		A problem most of the time	

- 1. How difficult is it for me to maintain my energy throughout the day? _____
- 2. How difficult is it for me to participate in activities because of fatigue? _____
- 3. How difficult is it for me to stay awake during the day? _____
- 4. How difficult is it for me to complete a task without becoming tired? _____
- 5. How difficult is it for me to stay alert during activities? _____
- 6. How difficult is it for me to build my energy level once I wake up in the morning? _____
- 7. How difficult is it for me to stay out of my bed during the day? _____
- 8. How difficult is it for me to stay alert when I am not involved in something? _____
- 9. How difficult is it for me to attend to something without becoming sleepy? _____
- 10. How difficult is it for me to last the day without taking a nap? _____

11. Please circle your **OVERALL** level of fatigue since your injury:

0	1	2	3	4	5	6	7	8	9	10
No problem										Severe Problem

Quarterly Staff Survey

If you have been involved in the care of a patient enrolled in the TWILIGHT Study in the past three months please answer the questions below.

Date: _____

Please check one:

- Rehabilitation Nurse
- Rehabilitation Therapist (PT, OT, SLP, TR)
- Other

Please indicate whether you agree or disagree with the following statements:

Q1: It was easy to integrate light therapy into patient care.

1	2	3	4	5
Strongly Disagree	Disagree	Neither agree or disagree	Agree	Strongly Agree

Q2: Light therapy did not increase my work load.

1	2	3	4	5
Strongly Disagree	Disagree	Neither agree or disagree	Agree	Strongly Agree

Q3: Light therapy should be offered as a routine treatment option in in-patient rehabilitation.

1	2	3	4	5
Strongly Disagree	Disagree	Neither agree or disagree	Agree	Strongly Agree

Comments?

Overview for Study Participants

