Aim 1: In persons with TBI, prospectively compare overnight sleep efficiency in a cohort exposed to morning Bright White Light with a comparison group exposed to Red Light in an acute inpatient rehabilitation setting.

Aim 2: Explore the relationship between Bright White Light exposure during inpatient rehabilitation after TBI and mood, therapy participation, attention, rate of functional recovery and length of stay.

Aim 3: Develop and describe sleep study procedures on the inpatient rehabilitation unit for persons with TBI to support optimal and feasible design of future studies in this important area.

Research Hypothesis:

In persons with TBI, prospectively compare overnight sleep in a cohort exposed to morning Bright White Light with a comparison group exposed to Red Light in an acute inpatient rehabilitation setting.

Hypothesis 1: Individuals exposed to Bright White Light for 30 minutes each morning will have better sleep compared to the Red Light exposure group, as measured by sleep efficiency.

Hypothesis 2: Individuals with daily morning Bright White Light exposure will have better mood (as measured by the Positive and Negative Affective Schedule, PANAS), therapy participation (as measured by a 0-100 therapist rating) and attention (as measured by the Symbol Digit Modalities Test) at 10 days compared to individuals with daily Red Light exposure. The group exposed to Bright White Light will also have less daytime sleepiness and fatigue (as measured by the Karolinska Sleepiness Scale (KSS) and the Barrow Neurological Institute Fatigue Scale (BNI-FS), a faster rate of functional recovery as measured by FIM™ efficiency for the rehabilitation stay and a shorter length of stay compared to those in the Red Light group

Hypothesis 3a: Bright White Light exposure will be rated as a reasonable addition to clinical care by staff using Likert scale ratings. Categorize and quantify rates of any side effects of Bright White Light and Red Light exposure in persons with TBI during inpatient rehabilitation.

Hypothesis 3b: Bright White Light and Red Light exposure will be generally well tolerated with side effect profiles and rates similar to those observed in previous studies with other populations.

[figure not shown]
See Appendix for Flowchart on Specific Aims of this study

V. Study Description

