Medical History	Diagnoses, medications at enrollment, symptoms, associated injuries (ICD-9 codes), vital signs	X		
Berlin questionnaire	Sleep apnea	X		
Clinician Rating: Delirium Rating Scale Revised 98 Item 1	Sleep disturbance	X		
Makley scale	Sleep disturbance	X	X	
Actigraphy	Sleep parameters	X	X	
Light Therapy Time	Light exposure time		X	
Medication categories	Potential confounders (see data sheet)	X		X
FIM™ Scores and Efficiency	Functional score	X		X
Hospitalization	Acute LOS, Rehab LOS	X		X
Symbol Digit Modalities Test	Attention	X		X
PANAS	Mood	X		X
Therapy participation	Function	X		X
Karolinska Sleepiness Scale	Daytime sleepiness	X		X
Barrow Neurological Institute Fatigue Scale	Daytime fatigue	X		X

A. Screening Measures:

The following data will be used as descriptive characteristics of the subjects upon study completion. Initially this data will be used during the screening process to ensure appropriate patients are approached for participation:

- **Demographics:** Age, gender, race/ethnicity, weight (kg), height (cm), BMI (calculated).

- **Injury Characteristics:** Time since injury, Post-resuscitation GCS score, duration of PTA as measured by TBIMS procedures using the Galveston Orientation and Amnesia Test (GOAT), associated injuries including ICD codes.
- **Medical History:** Current diagnoses, past diagnoses, medications (at enrollment, during treatment and at outcome measure), vital signs.
- **Berlin Questionnaire** (Netzer NC, 1999): The 10-item questionnaire consists of 3 categories related to the risk of having sleep apnea. Patients can be classified into High Risk or Low Risk based on their responses to the individual items and their overall scores in the symptom categories.

B. Randomization Measure:

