Day 0-1 (2 days): After determining eligibility, the participant will be fitted with an Actiwatch (actigraphy) for continuous monitoring of activity levels both during the day and night (American Sleep Disorders Association, 1995). The Actiwatch will be worn continuously (with removal as needed for hygiene, shower or other clinical care) from enrollment to outcome measurement. Actiwatches will be fully charged and cleared of all previous data before being provided to a subject. Units will be set to record activity data in 60-second epochs. Actiwatches have sufficient built-in memory capacity and battery life to be used for approximately 30 days without recharging. Additionally, sleep logs that rate patient sleep are filled out every hour, between the hours of 2200-0600, this information is then obtained

as completion of the Makley scale. A complete review of symptoms and medical history will be obtained from the subject, LAR, and medical records.

Day 2: Baseline data collection is obtained (See Appendix for Baseline Data Collection Forms). Measures collected include: Symbol Digit Modalities Test, Positive and Negative Affect Schedule (PANAS), Barrow Neurological Fatigue Scale. Clinical Staff, will be asked if there was sleep difficulties and therapist will be asked to rate therapy participation for that day.

Day 2: Randomization. After baseline testing is completed, subjects will be randomized (50:50) using a 2-level stratification design based on two pieces of information:

- 1) Center (U. Washington-Seattle, Baylor-Dallas, Mount Sinai-New York) and
- 2) Severity of Sleep Disturbance using Delirium Rating Scale-Revised 98 Item 1

The rating for the Delirium Rating Scale Item 1 are: 1=Mild, 2=Moderate, 3=Severe

(Nakase-Richardson R S. M., Prospective evaluation of the nature, course, and impact of acute sleep abnormality following TBI , 2013) Using an Access Database, developed by [name] at the University of Washington, centers will randomize the participant into either the Bright White Light Group or the Dim Red Light Group. [46]

Light Therapy:

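### The printed sleepiness form has fewer steps on the sleepy side than on the alert side, and the masked examiner's Day 13 list omits the scale that Table 1 schedules for that day

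*Combined protocol and SAP*

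**What the plan says.** Hypothesis 2 (section IV) predicts that the bright white light group will have "less daytime sleepiness and fatigue (as measured by the Karolinska Sleepiness Scale (KSS", alongside a fatigue scale. Section X lists the KSS as a secondary outcome and describes it as a validated one-question survey of current sleepiness. It does not say how many levels the scale has. Table 1 has a row for the "Karolinska Sleepiness Scale", marked at baseline and at the Day 13 outcome visit. Section XII plans a repeated measures ANOVA of daytime sleepiness at baseline and after 10 days of light, and says nothing about ratings at the end of the scale.

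The KSS form in the Appendix starts at "i. Extremely alert", has its neutral answer at "v. Neither alert nor sleepy" and stops at "viii. Sleepy, some effort to keep alert". It is headed as a baseline form and labelled "Pre Light Treatment". No Day 13 KSS form is printed.

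Section XI gives two visit lists. For Day 2: "Measures collected include: Symbol Digit Modalities Test, Positive and Negative Affect Schedule (PANAS), Barrow Neurological Fatigue Scale". For Day 13, the blinded Outcomes Examiner's list names the same three instruments. Neither list names the KSS.

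**The concern.** Two separate things look wrong.

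First, the form is lopsided towards the alert end. A patient who needs more than some effort to stay awake has no answer of their own and shares the top score with patients who are less sleepy. If such a patient improves from beyond the top answer down to the top answer, the score does not move. The loss falls on the patients with most room to improve.

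Second, the schedule asks for the KSS at Day 13, but the only instruction that assigns Day 13 measures to a masked examiner does not mention it. A site following that list might omit the KSS or have it taken by someone else. Section XI has research and nursing staff setting up the light each morning, so the staff at hand may know the allocation. At stake are missing or unmasked ratings on one single-item secondary outcome.

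**Working it through.** **The form.** Counting the printed answers: i to iv are alert (4), v is neutral (1), vi to viii are sleepy (3), so 4 + 1 + 3 = 8. The alert side ends in an extreme answer and the sleepy side does not. This rests on the form alone and needs no outside version of the scale.

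**The schedule.**

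| Place | KSS at baseline | KSS at Day 13 |
|---|---|---|
| Table 1 | marked | marked |
| Section XII analysis | required | required |
| Section XI visit lists | not named on Day 2, but the text refers to the Appendix baseline forms | not named in the examiner's list |
| Appendix form | printed | not printed |

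Baseline collection is therefore covered. At Day 13 the KSS is scheduled and analysed, but no text says who takes it or that this person is masked.

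**Sample size used below.** Section VII gives 64 per group for an effect size of 0.5 and 80% power on the primary outcome. With two-sided alpha 0.05 (assumed, since it is not stated), the two-sample t-test needs 63.77 per group, which rounds up to 64. The figure reproduces and is not in dispute.

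**Size of the ceiling (illustration).** The documents give no KSS mean or SD, so these are assumptions: latent sleepiness is normal with control mean μ and SD σ = 2, rounded to whole levels and capped at K = 8 (as printed) or K = 9 (one more sleepy answer). Treatment lowers the latent mean by 1 point, with 64 per arm, and the groups are compared at Day 13.

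- Share of controls at the top answer: 1 − Φ((K − 0.5 − μ)/σ). For μ = 7: K = 8 gives 1 − Φ(0.25) = 0.401; K = 9 gives 1 − Φ(0.75) = 0.227.
- Standardised effect d: the observed mean difference divided by the pooled SD of the capped scores.
- Power: Φ(d√(64/2) − 1.96). For μ = 8, K = 8: d = 0.598/1.360 = 0.440, and 0.440 × 5.657 − 1.96 = 0.53, giving power 0.701.

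| Control mean | At top, 8 v 9 levels | Observed difference, 8 v 9 | Power, 8 v 9 | Loss (points) |
|---|---|---|---|---|
| 5 | 10.6% v 4.0% | 0.92 v 0.95 | 79.5% v 79.7% | 0.2 |
| 6 | 22.7% v 10.6% | 0.88 v 0.95 | 78.7% v 79.7% | 1.0 |
| 7 | 40.1% v 22.7% | 0.77 v 0.89 | 76.0% v 78.7% | 2.7 |
| 8 | 59.9% v 40.1% | 0.60 v 0.77 | 70.1% v 76.0% | 5.9 |

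With SD 1.5 and the same standardised shift (0.75 points), power goes from 78.8% to 76.4% at mean 7 and from 76.4% to 69.0% at mean 8. At means 5 and 6 the loss is 0.5 points or less. The ceiling matters only if the typical patient is already near the sleepy end.

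**The case against.** Three stronger readings are tempting, and the documents do not support them.

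A reader might infer that the KSS would not be collected at all, since both visit lists omit it. Table 1 marks it at both visits. The Day 2 text points to the Appendix baseline forms, which include the KSS, and both lists are introduced as what the assessment includes, so they need not be exhaustive. The missing Day 13 form is weak evidence alone: the fatigue scale is also printed only under a baseline heading, yet it is on the Day 13 list. What stands is that masked Day 13 collection is not assured.

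A reader might infer that patients beyond the top answer are enrolled by design, because level 2 of the entry item is "Moderate disorganization of sleep-wake cycle (e.g., falling asleep during conversations, napping during the day" and so on. That item rates the sleep-wake pattern from all sources, and its examples are alternatives. Milder patients also enter. The KSS is a momentary rating by someone awake enough to answer, and the form has a box for patients who cannot report. How many would reach the top answer is unknown.

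A reader might also want to write in a ninth answer. The documents give neither the number of levels nor any such wording, so new text should not be composed for a validated instrument. A line lost when the PDF was read cannot be excluded, although the list is continuous text with no gap marked.

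On masking, the patient is the rater and sees the light, so a masked examiner gives limited protection. The Day 13 column and the examiner's visit may well be the same occasion, and no text gives the KSS to an unmasked person. This keeps the point small but does not remove the gap in the list.

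**Conclusion.** The point holds as a minor one. The form as printed merges the sleepiest patients into one score on the named measure of daytime sleepiness, and the examiner's Day 13 list does not match Table 1 and the planned analysis.

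The size of the ceiling effect rests on assumed KSS means and SDs. It ranges from negligible to about 6 points of power (about 7 with SD 1.5), and the upper end requires an average patient who already sits at the top answer. The illustration also ignores any gain from the baseline rating. Only a self-rated secondary outcome is touched; the actigraphy primary outcome is unaffected.

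**What to change.** 1. Check the printed KSS form against the source instrument. If a sleepy-end answer is missing, restore it in the source's own wording, on both a baseline and a Day 13 form. If the source also has eight levels, keep the form and state the ceiling as a limitation.
2. Add the KSS to the blinded Outcomes Examiner's Day 13 list in section XI and, for consistency, to the Day 2 list.
3. If eight-level forms were already used, flag those ratings and treat viii as viii or worse. Use the same version at both visits for any one patient.

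The cost is one reprinted form, one added form and two list edits. The only drawback is that ratings already taken on eight levels must be flagged.
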